#### Which Committee will review this protocol?

- ☒ The Psychosocial Behavioral and Health Services Research Committee (PBHSRC)

## Protocol Body

### 1.0 Rationale

Lung cancer is the second most common cancer in men and women, and the leading cause of cancer deaths in the US.[1] The American Cancer Society estimates that about 228,000 Americans will be diagnosed with lung cancer, and about 160,000 Americans will die of lung cancer this year.[1] Five-year survival rates are only about 16.6%, in part related to patients having advanced disease at the time of diagnosis.[2] Smoking is by far the most important risk factor for developing and dying from lung cancer. It is estimated that cigarette smoking causes about 90% of all lung cancers in the United States.[1, 3] Tobacco use is the #1 modifiable risk factor for death in the US, accounting for over 400,000 deaths annually. The morbidity associated with smoking is substantial. Tobacco use is associated with countless chronic health problems for smokers and others exposed to second hand smoke, including heart and lung disease.[4, 5]

In June 2011, the National Lung Screening Trial (NLST) published its primary findings. This landmark study found 20% fewer lung cancer deaths among current and former heavy smokers who were screened with low dose computed tomography (LDCT) compared to those who received standard chest x-rays.[6] Current estimates are that over 12,000 lung cancer deaths would be prevented each year if heavy smokers were screened annually.[7] The NLST findings were met with much fanfare in the media and were quickly followed by marketing campaigns promoting computed tomography (CT) scans for high-risk smokers. In fact, groups with an economic interest in testing had already begun offering CT screening for lung cancer after preliminary results of the NLST were released in November 2010.[8]

Yet, LDCT screening for lung cancer is not without risks, most notably, radiation exposure and a high false-positive rate leading to subsequent follow-up and testing with its own associated harms. For the individual, the benefit of being screened for lung cancer with LDCT must be weighed against the potential harms: receiving false results, radiation exposure, and the risk of over diagnosis.[6, 9] A recent systematic review of evidence regarding the benefits and harms of LDCT screening for lung cancer confirmed the results of the NLST while raising concerns about the potential harms of screening.[10] The rate of positive results in each round of screening was 20% while only 1% of patients were found to have lung cancer. Overall, patients who completed all three screens had a 40% chance of having at least 1 abnormal result, requiring additional surveillance and diagnostic workup.

The need for patient decision aids to support informed decision making for lung cancer screening with LDCT is growing dramatically. Evidence-based guidelines have been released endorsing LDCT scans for high risk smokers, while emphasizing the importance of making an informed decision about screening within the context of receiving smoking cessation services for people who continue to smoke.[10, 11] We know from our preliminary study (Protocol PA11-0626) that patients are interested in the topic, know very little of lung cancer screening and the potential harms and benefits, and want decision support tools.[12] In addition, insurers are increasingly covering

LDCT scans for lung cancer screening among patients meeting criteria consistent with the NLST. The US Preventive Services Task Force has issued a guideline endorsing annual screening with LDCT.[13] If followed by Medicaid and Medicare coverage, this would greatly increase the pool of high risk individuals able to receive the scans without copays. Thus, lung cancer screening is rapidly becoming a viable secondary preventive service for many heavy smokers, and there is a great need for quality, evidenced-based patient decision support to help patients make informed screening decisions.

The Patient-Centered Outcomes Research Institute (PCORI), an independent non-profit research organization established under the 2010 Patient Protection and Affordable Care Act,[14] has recognized this need. PCORI has awarded a contract to [name] to update and evaluate a patient decision aid which promotes informed decision making about lung cancer screening with LDCT. This project, CER-1306-03385 “Promoting Informed Decisions about Lung Cancer Screening,” is in line with PCORI's mission to help people make informed healthcare decisions. The research plan was funded after peer review (attached as Appendix E).

## **2.0 Objectives**

This protocol addresses the second phase of a larger project funded by the Patient-Centered Outcomes Research Institute to help heavy smokers make informed decisions about lung cancer screening with low-dose computed tomography (LDCT).

This is an educational research study. Patients of state-based tobacco quitlines will receive educational materials about lung cancer screening to help them understand the potential benefits and harms of screening. This is not a study to evaluate the outcomes of screening for lung cancer.

Our quitline partners for this study are tobacco cessation counseling service providers who operate state-based quitlines as members of the North American Quitline Consortium. Patients for this study will therefore be quitline patients from participating states where these partners have contracts to provide services. This expands on our initial quitline partner, Information & Quality Healthcare (IQH).

The aim of this phase is to compare outcomes for promoting informed screening decisions about lung cancer screening in a randomized trial of patients who smoke recruited through state-based smoking cessation quitlines, where patients will be randomly assigned to the updated patient decision aid or to standard educational materials on lung cancer screening.

We will test several hypotheses related to the use of the patient decision aid in promoting informed decisions about lung cancer screening. Specifically, compared to heavy smokers who receive standard educational materials which lack an emphasis on making an informed decision, heavy smokers who view the patient decision aid about lung cancer screening will report:

1. being more prepared to make a decision about lung cancer screening,

2. feeling more informed about the screening decision, and
3. being clearer about their values related to the tradeoffs between benefits and risks of lung cancer screening with LDCT.

We further hypothesize that heavy smokers who view the decision aid will be more knowledgeable about lung cancer screening than patients receiving the standard educational materials. We will also collect data about screening intentions and completion of screening for exploratory purposes. We make no a priori hypotheses about these latter outcomes because the literature on the impact of decision aids on cancer screening uptake is mixed.

### **3.0 Eligibility of Subjects**

#### Inclusion Criteria:

1. Men and women 55 to 77 years of age.
2. Participants must speak English.
3. Current smoker or quit smoking within the past 15 years.
4. At least a 30 pack-year smoking history

#### Exclusion Criterion:

1. History of lung cancer.

[figure not shown]
#### Age Justification:

The Centers for Medicare and Medicaid Services (CMS) coverage guidelines for lung cancer screening include people 55 to 77 years of age. [18]

### **4.0 Research Plan and Methods**

The design for this study is a randomized trial with quitline patients recruited through state-based quitlines. Patients will be randomly assigned to the patient decision aid (200 patients) or standard educational information about lung cancer screening (200 patients). (Note that based on our estimates of attrition, up to 550 patients may be enrolled in the study to achieve a final sample of 400.) The design includes a pre-test assessment with a subscale of the knowledge measure developed for this study, an assessment at 1-week to collect data on the outcomes for the study and a 3-month follow-up to determine how well patients retain the information and track any use of screening services. A 6-month follow-up assessment will also be conducted on a subsample of the patients to track lung cancer screening rates via patient report.

#### Schema for the Randomized Trial

### Recruitment Strategies

Subjects for this study will be patients referred by tobacco quitlines in states that have contracts with our quitline partners for provision of smoking cessation services. Thus, identification of patients for the study will be coordinated through the quitline service providers. Recruitment will occur over 24 months, starting in month 7 of year 1.

Our quitline partners will identify potential participants between the ages of 55 and 77. These may be new referrals for smoking cessation services (includes self-referrals and patients referred by primary care physicians and other health providers) or patients who are already registered with the quitline. MD Anderson will not receive patient lists from the quitline service providers. Rather, these quitline partners will send invitation materials directly to their patients.

Quitline staff members will mail potential participants invitation materials describing the research study or email them a Portable Document Format file (PDF) of the invitation materials. See the invitation letter in appendix F, the recruitment flyer in appendix G, and the IRB advertisement approval form in appendix H. The invitation letterhead and signature will be customized for each quitline partner.

An invitation letter and recruitment flyer will be placed in a QuitKit sent to new referrals at IQH. The QuitKits include information about the different kinds of services provided (e.g., phone counseling, web-based information), how to access the services, and other resources available to patients to help them with quit smoking. IQH staff members may also use the IQH script in Appendix R to inform new referrals about the study by phone.

The recruitment strategy may vary between quitlines. Like IQH, some quitlines may choose to mention the study by phone in addition to sending invitation materials. Other quitlines may choose to inform patients of our study solely by phone (see the quitline recruitment script in appendix Q).

The recruitment materials will provide a toll free telephone number and an email

address that patients can use to contact the research team about participation. When patients receive the materials and are interested in participating, they will contact MD Anderson staff who will assess their eligibility.

#### Eligibility Assessment, Informed Consent, and Randomization

Patients with an interest in the study will be given information to contact the research team about participation. Research staff will provide a description of the study using a recruitment script (appendix I) and assess the patients' eligibility following the study eligibility criteria using a screening form (appendix J). These forms will be kept for all individuals screened including screen-failures and used for aggregate reporting of eligibility. We propose to collect informed consent from patients via telephone. See Section 7 for details about the verbal consent process and request for waiver of written authorization for the study. Contact information (appendix I) and patient characteristics (see baseline survey in appendix K) will be collected at that time. Eligible, consented patients will then be allocated to receive the patient decision aid or standard educational materials using the procedure described under "Allocation Strategy." Randomization will be done within each state organization (i.e., pre-stratification by state quitline) to control for any systematic differences in clients served.

Patients will be mailed the study materials for review. Patients will be instructed to review the materials – patient decision aid or standard educational materials – over the following week. A link to the current patient decision aid and standard educational materials can be found in appendix L. Because the patient decision aid is a video, during the eligibility assessment we will ask patients if they have access to a DVD player or computer with a DVD drive for viewing the aid. We will also make the aid available for viewing on the Internet. If patients do not have access to a DVD player or have Internet access, we will facilitate their finding access locally (e.g., public libraries). In the data analysis phase, we will examine any differences in the study outcomes across the different modes for delivering the decision aid and adjust for these as needed.

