#### Analysis plan

Patients' demographic characteristics at baseline will be summarized using descriptive statistics such as mean, standard deviation, median, interquartile range (IQR), and frequency where appropriate. We will apply Student t-test/Wilcoxon test and Kruskal-Wallis test/analysis of variance (ANOVA) to compare continuous variables between arms, and the chi-square test or the Fisher's exact test to assess the differences of categorical variables between arms.[16]

As primary analysis, we will perform two-sided two group t-test to compare the differences of the three primary endpoints between the two arms. We will perform similar analysis on knowledge scores. For these efficacy endpoints, intend-to-treat analysis will be applied to the participants. We will look at the impact of race/ethnicity (African American vs. Caucasian) on the relationship between the outcomes and lung cancer screening materials using general linear regression. We will also assess the interaction between intervention and race/ethnicity using linear regression model to examine whether or not the decision aid has differential effects between African Americans and Caucasians by testing.

We will use two-sided two group t-test to compare the change of knowledge scores from baseline to post intervention between the two arms. Since the knowledge outcome will be assessed at week 1 and then 3-month and 6-month follow-ups, linear mixed effect models for longitudinal measures[17] will be employed to assess the change in the magnitude of the outcomes over time adjusting for multiple covariates including intervention indicator, age, gender, race, education level, insurance status, and other factors. We may also look at the interaction between intervention and time. Appropriate transformation of the measures will be used in the analyses to satisfy the normality assumption of linear mixed effect model. Mode of administration and completion of intervention/control materials (i.e., dose/exposure) will be tracked to account for their

effects.

We will also estimate the lung cancer screening rate within each arm along with 95% confidence interval. Chi-square test will be used to assess the differences of the lung cancer screening rates between arms.

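### Arm comparisons may be adjusted for viewing mode and completion of the materials, both of which arise after randomisation; the primary unadjusted tests are not affected

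*Combined protocol and SAP*

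**What the plan says.** Two statements bear on this point.

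- Section 4.0 (Eligibility Assessment, Informed Consent, and Randomization), on viewing modes: "we will examine any differences in the study outcomes across the different modes for delivering the decision aid and adjust for these as needed". It gives no model and no criterion for when adjustment is needed, and it does not say which outcomes are meant.
- Section 5.0 (Analysis plan), at the end of the paragraph on knowledge change scores and the longitudinal knowledge model: "Mode of administration and completion of intervention/control materials (i.e., dose/exposure) will be tracked to account for their" effects. That model's covariate list is also open-ended.

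The order of events is clear from Section 4.0. First comes screening, when "during the eligibility assessment we will ask patients if they have access to a DVD player or computer with a DVD drive". Then "Eligible, consented patients will then be allocated to receive the patient decision aid or standard educational materials". Only after the mailing is there anything to view or complete: "Patients will be instructed to review the materials" over the next week. The alternative viewing route is described for the aid alone: "We will also make the aid available for viewing on the Internet".

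The primary analysis is separate: "we will perform two-sided two group t-test to compare the differences of the three primary endpoints between the two arms". The Analysis plan applies intention to treat to these endpoints and to knowledge.

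**The concern.** Randomisation makes the arms comparable in everything fixed before allocation. It gives no such protection once the comparison is conditioned on something that happens afterwards.

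- **Completion** can depend on arm (a video against other materials) and on the patient's engagement, and it lies on the path from the materials to the outcome. Holding it fixed compares aid and control patients who differ in engagement, and removes or distorts part of the effect of interest.
- **Viewing mode** has no counterpart among controls. A mode term in a two-arm model turns the arm coefficient into a contrast of aid patients who used the reference mode with all controls. That is a self-selected group against a randomised one.
- **The trigger** for the mode adjustment appears to be an observed difference in outcomes, so the data would decide whether it is made.

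At stake is whether the adjusted and secondary results, chiefly knowledge over time, can be read as effects of being assigned the aid.

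**Working it through.** **1. The plan's own figure.** Section 5.0 gives 190 per arm, difference 5, SD 15 and two-sided alpha 0.017. The standardised difference is 5 / (15 × √(2/190)) = 3.249, and the critical value is 2.387. Power = Φ(3.249 − 2.387) = 0.806, or 0.802 with the noncentral t. The stated 80% reproduces. It belongs to the unadjusted test, so nothing below changes it.

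**2. Formula for completion.** When a yes/no completion term is added to a regression on arm:

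adjusted effect = unadjusted effect − b × (pA − pC)

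Here pA and pC are the completion rates in the aid and control arms, and b is the pooled within-arm slope of outcome on completion. If pA = pC, the two estimates agree whatever b is. This covers a single additive term only, not a completers-only analysis or an arm-by-completion interaction.

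**3. Illustrative inputs (assumptions, not in the documents).** Unmeasured engagement lowers the decisional conflict score by 5 points per SD (total SD 15; lower is better) and raises completion by a log-odds of 1.0 per SD. By numerical integration, the within-arm covariance of engagement and completion is 0.199 at 60% completion and 0.160 at 75%. The completion variances are 0.60 × 0.40 = 0.240 and 0.75 × 0.25 = 0.1875.

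*No true effect, 60% aid and 75% control.* b = −5 × (0.199 + 0.160) / (0.240 + 0.1875) = −4.20. Adjusted effect = 0 − (−4.20)(−0.15) = **−0.63**.

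*The aid lowers the score by 8 points in those who complete it, same rates.* ITT effect = −8 × 0.60 = −4.8. b = (−1.795 − 8 × 0.240) / 0.4275 = −8.69. Adjusted effect = −4.8 − 8.69 × 0.15 = **−6.10**, and 6.10 / 4.8 = 1.27.

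*Same effect, rates reversed (75% aid, 60% control).* ITT effect = −6.0. b = (−1.795 − 8 × 0.1875) / 0.4275 = −7.71. Adjusted effect = −6.0 + 7.71 × 0.15 = **−4.84**, about 19% too small.

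Simulation at 200 per arm agrees: −0.6, −6.1 and −4.9. Under the null, rejection at 0.017 rises from 0.016 to 0.031 at 60%/75%.

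**4. Range under a second set of assumptions.** Engagement correlates 0.5 with completion propensity and 0.3 to 0.5 with the outcome; 200 per arm.

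| True ITT effect | Completion, aid/control | Adjusted estimate | Rejection at 0.017 |
|---|---|---|---|
| 0 | 70% / 70% | near 0 | 0.015 to 0.017 |
| 0 | 60% / 80% | −0.8 to −1.2 | 0.04 to 0.06 |
| 0 | 50% / 90% | −1.5 to −2.6 | 0.06 to 0.20 |
| −5 | 60% / 80% | −6.8 to −7.3 | not computed |
| −5 | 80% / 80% | about −5.0 | not computed |
| −5 | 80% / 60% | −3.3 to −3.8 | not computed |

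The unadjusted estimate stayed within 0.1 of the true value throughout.

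**5. Viewing mode.** With a mode term present only in the aid arm, the arm coefficient is the mean of reference-mode aid patients minus the mean of all controls. Assume no true effect, half of aid patients using each mode, and engagement shifting mode choice by a log-odds of 1.0 per SD. Mean engagement in the reference-mode group is then −0.413 SD, so the coefficient is −5 × (−0.413) = **+2.1 points**. Simulated rejection at 0.017 is about 10%.

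**6. Knowledge scale.** The stated SDs of 19.36 and 15.76 give an average SD of √((19.36² + 15.76²)/2) = 17.65. If engagement is related to knowledge to the same standardised degree, the null shift at 60%/75% is 0.63/15 × 17.65 = 0.74 points in size, against the planned 5.75. Higher knowledge is better, so it would again favour the aid.

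**The case against.** The strongest reply is that the trial's main result is already protected. The three primary endpoints are tested by t-tests, which have no covariates, under intention to treat, and the sample size rests on those tests. The tracking sentence sits in the knowledge paragraph, and knowledge is secondary. **This stands.** A reader might infer that the primary comparison is compromised, or that an adjusted estimate would rival it as the trial's answer. The documents support neither: the primary analysis is named, and no text gives an adjusted estimate that standing. Nor does the plan state that the primary outcomes will be regressed on completion.

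Second, looking for differences across modes of delivering the aid is most naturally a comparison within the aid arm, which is legitimate. **This stands for the examining, not for the adjusting.** Section 4.0 speaks of study outcomes generally and exempts none.

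Third, mode may be partly fixed at baseline, since "Because the patient decision aid is a video, during the eligibility assessment we will ask patients if they have access to a DVD player"; or mode of administration may mean a telephone or mailed questionnaire, since Section 4.0 allows both. **This does not rescue the adjustment.** Access is not the mode used, and the questionnaire route is also settled after allocation.

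Fourth, the sizes are assumed and can be small: −0.63 is 13% of the planned 5-point difference and 0.42 of a standard error (15 × √(2/200) = 1.5). **This stands** and limits how strongly the point can be put. It is no reason to keep an adjustment that offers no gain to set against the risk.

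**Conclusion.** The point holds in a limited form. Both statements allow an arm effect to be adjusted for variables that arise after randomisation, one of which exists in only one arm. Such an estimate is not a randomised comparison and is inconsistent with the intention-to-treat principle that the plan applies to its efficacy endpoints. The exposure is greatest in the knowledge change and longitudinal analyses; the primary t-tests and their power are unaffected.

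That conclusion follows from the order of events in Section 4.0 and needs no assumed figure. The size does. For a single additive completion term, the shift is near zero when completion is equal. At 60%/75% it is about −0.6 points under the null, and about 27% inflation of a −4.8 effect. It becomes attenuation when the rates are reversed, and it grows as the rates diverge. The documents give no completion rates, so neither direction nor size can be predicted for this trial.

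**What to change.** Replace both statements with one rule:

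- No arm comparison, including the knowledge mixed model, is adjusted for the mode used or for completion. The unadjusted or baseline-covariate-adjusted ITT effect is the only confirmatory estimate.
- Mode is reported descriptively within the decision-aid arm and completion by arm, both labelled non-randomised.
- If access matters, use the DVD-access answer asked at eligibility as a baseline covariate, provided it is retained as an analysis variable. The screening form is not in the text available, and Section 4.0 does not clearly say that Internet access is asked of everyone.
- Any exposure analysis is labelled exploratory, with its method and assumptions named. If a complier-average effect is estimated with arm as the instrument, state that the exclusion restriction is doubtful. Controls also receive active materials, so someone who would not complete the aid may still be affected by which materials they are assigned.

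The cost is wording in Sections 4.0 and 5.0. Sample size is unchanged, and no new data are needed if the access answer is already kept.
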